6.2. Planned Summary Display Details

Subjects who have multiple subject numbers (i.e. rescreened subjects) will be analyzed as unique subjects based on the latest screening results (see Section 15.6.1 and Section 15.6.2).

The definition of subgroup is described in Section 5.4.2.

• Subject Disposition

Subject Status and Reason for Study Withdrawal

The number and percentage of subjects completing the study (see Appendix 7) or withdrawing early from the study will be summarized overall and by reason for withdrawal by treatment group and total. Reasons for withdrawal of subjects will be listed.

Treatment Status and Reasons for Discontinuation of Study Treatment

The number and percentage of subjects completing the treatment or discontinuing the treatment during the study will be summarized overall and by reason (and subreason) by

treatment group and total. Reasons for discontinuation of study treatment of subjects will be listed.

Screening Status and Reasons for Screen Failure

The number and percentage of subjects who passed screening (i.e. enrolled) and who failed screening and were therefore not entered into the study will be summarized regardless of treatment group. Note that the reasons for rescreen subjects who initially failed but subsequently enrolled are not included in the display (see Section 15.6.2). Reasons for screen failure of subjects will be listed.

Subjects Enrolled by Country and Site ID

The number and percentage of subjects by Country and Site ID and Investigator name will be summarized by treatment group and total.

- **Protocol Deviations**

Important Protocol Deviations

The number and percentage of subjects who had important protocol deviations defined in PDMP will be summarized by treatment group and total. Important protocol deviations of subjects will be listed.

Subjects with Inclusion/Exclusion Criteria Deviations

The number and percentage of subjects, who were randomized into the trial, but deviated from the inclusion or exclusion criteria, will be summarized, further classifying inclusion/exclusion deviations by treatment group and total. Inclusion/exclusion criteria deviation of subjects will be listed.

- **Population Analyzed**

Study Populations

The number and percentage of subjects in each analysis population (defined in Section 4) will be summarized by treatment group and total.

Exclusion from the Per Protocol Population

The number of the exclusions from the PP population and the exclusion categories will be summarized by treatment group and total.

Composition of the Randomized Population

The number and percentage of subjects by dialysis, cohort, and prior ESA use will be summarized by treatment group and total.

- **Demographic and Baseline Characteristics**

Demographic Characteristics

The number and percentage of subjects or summary statistics will be provided by treatment group and total for the demographic and baseline characteristics: Sex, Age (years), Age Group (years), Ethnicity, Race detail, Height, Weight, Body Mass Index, and CKD Stage. The period of time on dialysis (years) will also be summarized only for PD subjects in Safety population and Efficacy PD population. Age Group (years) will be categorized into 3 ('≤18', '19-64', '≥65'). CKD Stage will be categorized into 3 by eGFR (Stage 3 (30= \leq eGFR<60), Stage 4 (15= \leq eGFR<30), Stage 5 (eGFR <15)) at a screening visit. Separate summaries for ITT, Safety, Efficacy ND, and Efficacy PD population will be produced. For Efficacy ND population, summary will also be provided by cohort. For the ITT, Safety, and Efficacy PD populations, summary will also be provided by Prior ESA-use.

Prior ESA

For overall prior ESA medication, the weekly dose (standardized by IU/week) erythropoietin resistance index (ERI), and the number and percentage of subjects' dosing route (intravenous [IV] or subcutaneous [SC]) will be summarized by treatment group and total. For each type of prior ESA medication (epoetin, epoetin beta pegol, and darbepoetin alfa), the weekly dose (IU/week or μ g/week), ERI and the number and percentage of subjects' dosing route (IV or SC) will also be summarized by treatment group and total. See Section 15.6.2 for the derivation of standardized weekly dose and ERI. Separate summaries for ITT and Safety population will be produced.

Age Ranges

The number and percentage of subjects within each age range category will be provided by treatment group and total. Age range will be categorized into: 18-64 years, ≥65-84 years, ≥85 years.

Race and Racial Combinations

Summaries of race and racial combinations will be provided by treatment group and total.

Family History for CV Risk Factors

A summary of family (first degree relatives) history for CV risk factors will be provided by treatment group and total.

Substance Use (History of Tobacco Use, Alcohol Intake)

A summary of substance use will be provided by treatment group and total.

- **Medical Conditions and Concomitant Medications**

Current/Past Medical Conditions

The number and percentage of subjects with current and past medical conditions recorded in eCRF will be provided by treatment group and total.

Concomitant Medications

The number and percentage of subjects reporting the use of each concomitant medication will be summarized by treatment group and total by anatomical therapeutic chemical (ATC) Level 1, and Ingredient. Summaries for pre-therapy, on-therapy, and post-therapy medication will be provided separately. See Section 15.4.1 for the study phases.

Other Concomitant Medications (On-Therapy ESA, iron, and anti-hypertensive medication)

The similar summary as above will be provided by treatment group and total focusing on on-therapy ESA, on-therapy iron medication (see Section 15.6.2), and on-therapy anti-hypertensive medications. See Section 15.4.1 for the study phases.

Blood Products and Blood Supportive Care Products (On-Therapy)

The number and percentage of subjects who use blood products and/or blood supportive care products will be provided by treatment group and total. The details for the use will also be summarized.

- **Exposure and Treatment Compliance**

Exposure to Study Treatment

Full details of exposure definition are presented in Section 15.6.2.

Time on study treatment (days), subject daily dose (for daprodustat) or monthly dose (for epoetin beta pegol), and cumulative dose will be summarized using the number of subjects exposed, mean, standard deviation, median, minimum, and maximum by treatment groups. Time on study treatment will be categorized in different time periods (< 3 months, 3 months to 6 months, >6 months to 12 months, >12 months; 1 month = 30.4375 days) and the number and percentage of subjects exposed will be displayed for each category.

Treatment Compliance

Full details of treatment compliance definition are presented in Section 15.6.2.

The number and percentage of subjects within each category will be summarized by treatment groups and total for up to Week 4, Week 40 to 52, and overall. Up to Week 2 and Week 2 to 4 will also be summarized for only cohort 3. The categories will be classified into under compliant, compliant, over compliant.

7. EFFICACY ANALYSES

7.1. Primary Efficacy Analyses

7.1.1. Endpoint / Variables

[Endpoint / Parameter/ Display Type]	Populati on	Absolute						
		Stats Analysis			Summary		Individual	
		T	F	L	T	F	F	L
Mean Hgb based on observed Hgb during the Primary Efficacy Evaluation Period (i.e. Individual Mean of Hgb at Week 40, 44, 48, and 52)								
(Preliminary assessment) Observed Case	mITT				Y			
Observed Case	Efficacy PD				Y			
Observed Case by Subgroup ^[3]	Efficacy PD				Y			
Model based Mean Hgb during the Primary Efficacy Evaluation Period								
(Primary) MMRM	ITT	Y	Y					
MMRM	mITT/PP /Efficacy ND	Y	Y					
MMRM By Subgroup	ITT	Y	Y ^{[1][2]}					
MMRM Excluding ESA Users with Hgb rapid increase at Week 2	ITT	Y	Y					
MMRM Evaluable Hgb	ITT	Y	Y					
Analysis of Covariance (ANCOVA)	mITT/PP	Y						
ANCOVA By Subgroup	mITT	Y	Y ^[1]					
Tipping Point Analysis	ITT/mITT /PP	Y	Y					

NOTES :

- T = Table, F = Figure, L = Listing, Y = Yes display generated.
- Stats Analysis = Represents TFL related to any formal statistical analyses (i.e. modelling) conducted.
- Summary = Represents TFL related to any summaries (i.e. descriptive statistics) of the observed raw data.
- Individual = Represents FL related to any displays of individual subject observed raw data.

[1] Forest Plots

[2] For prior ESA use, Hgb curve over time will also be displayed.

[3] Only for prior ESA use and baseline Hgb.

7.1.2. Summary Measure

Mean Hgb based on observed Hgb during the Primary Efficacy Evaluation Period

The values will be summarized using mean, standard deviation, 95%CI, minimum, P25, median, P75, and maximum by treatment group for the mITT and Efficacy PD population. For the Efficacy PD population, summary will also be provided by baseline Hgb.

Analysis of Mean Hgb during the Primary Efficacy Evaluation Period

For ITT population, model-based mean Hgb will be estimated using a statistical model (Section 7.1.5). The point estimates of model-based mean Hgb for each treatment will be presented with standard error, and 95% CI. For non-inferiority assessment at a one-sided significance level of 2.5%, the estimate of treatment difference, its 95% CI, and non-inferiority p-value will be provided. Analysis will be repeated by mITT, PP, Efficacy ND populations in the same manner. The subgroup analysis based on the ITT population will be also produced using tables and forest plot (See Section 7.1.5 for the detail).

Sensitivity/Supplementary analysis for Mean Hgb during the Primary Efficacy Evaluation Period

- Excluding ESA Users with Hgb rapid increase at Week 2

Supplementary analysis excluding the ESA users whose daprodustat dose level was decreased by one step at Week 2 will be performed as the same as primary efficacy analysis using a mixed model for repeated measures.

- Evaluable Hgb (Section 7.1.6.1 for the statistical analysis specifications)

Supplementary analysis using evaluable Hgb (See Section 15.6.3) based on the ITT population will be performed as the same as primary efficacy analysis using a mixed model for repeated measures.

- ANCOVA (Section 7.1.6.2 for the statistical analysis specifications)

Supplementary analysis using ANCOVA based on the mITT population will be summarized. Analysis will be repeated for the PP population. The subgroup analysis based on the mITT population will be produced using tables and a forest plot.

- Tipping Point Analysis (Section 7.1.6.3 for the statistical analysis specifications)

Tipping point sensitivity analysis based on the ITT population will be summarized using combined treatment differences, the associated 95% CIs and non-inferiority p-values by delta adjustments. Graphical display, the horizontal and vertical axes indicate values of delta for daprodustat and epoetin beta pegol, will be provided as a heat map that represents non-inferiority p-values obtained from the test conducted for each delta adjustment. The color grids which highlight non-inferiority success or not will be displayed.

7.1.3. Population of Interest

The primary efficacy analyses will be based on the ITT population, unless otherwise specified.

7.1.4. Strategy for Intercurrent (Post-Randomization) Events

Intercurrent events	Strategy
Study withdrawal	The following hypothetical scenario is considered; what would have happened if the event did not occur. The primary analyses using MMRM assume missing at random mechanism, that is the observations of missing depend on just observed values, not on unobserved values.
Prohibited medications (except for commercial ESA medications)	Basically, the occurrence of the event is taken to be irrelevant. Subjects with long-term use of prohibited medications will be excluded from the PP population.
Blood transfusion and/or commercial ESA medication	In primary analyses, the occurrence of the event is taken to be irrelevant.
Intermittent missing	The following hypothetical scenario is considered to assess what would have happened; if the event did not occur. The hypothesis is that an intermittent missing would occur at at-random manner, that is the observations of the missing depend on just observed values, not on unobserved values.

7.1.5. Statistical Analyses / Methods

Details of the planned displays are provided in [Appendix 10: List of Data Displays](#) and will be based on GSK data standards and statistical principles.

Unless otherwise specified, endpoints / variables defined in Section 7.1.1 will be summarized using descriptive statistics, graphically presented (where appropriate) and listed.

As a preliminary assessment, it will be confirmed whether the mean Hgb during the primary efficacy evaluation period in the daprodustat group would be in the target range (11.0-13.0 g/dL) at first. This confirmation will be established if the lower and upper limit of 95% CI for the mean Hgb based on observed Hgb during the primary efficacy evaluation period in the daprodustat group would lie fully within the target range. After the stated confirmation, non-inferiority will be assessed at a one-sided significance level of 2.5%.

7.1.5.1. Statistical Methodology Specification

Endpoint / Variables

 • Mean Hgb during the primary efficacy evaluation period (Weeks 40 to 52)
Model Specification

 • Analyses will be conducted by MMRM as follows: $Hgb_{ik} = \beta_0 + \beta_{baseline} * Baseline_i + \beta_j + \beta_k + \beta_{jk} + \beta_{baseline*k} * Baseline_i + \epsilon_{ik}$ 
Hgb_{i, week}: Hgb measurement for subject i at visit k β_0: Intercept $\beta_{baseline}$: baseline Hgb effect Baseline_i: Hgb measurement for subject i β_j: treatment effect (j= daprodustat, epoetin beta pegol) β_k: visit effect (k = Week 4, Week 8, ..., Week 52) β_{jk}: treatment-by-visit interaction $\beta_{baseline*k}$: baseline-by-visit interaction ϵ_{ik}: random error for subject i at visit k i: subject (i = 1, 2, ..., N) N: number of subjects included in the analysis
 • The model parameters will be estimated using Restricted Maximum Likelihood (method=REML) with the Newton-Raphson algorithm. • The Kenward-Roger method for calculating the denominator degree of freedom will be used. • The variance-covariance structures for repeated measures within the individual subject will be unstructured (type=UN). • LS means for treatment j at visit k will be calculated as follows. $\mu_{jk} = \beta_0 + \beta_{baseline} * \mu_{baseline} + \beta_j + \beta_k + \beta_{jk} + \beta_{baseline*k} * \mu_{baseline}$ 
μ_{jk}: LS mean for treatment j at visit k $\mu_{baseline}$: mean for baseline Hgb
 • Model based mean Hgb during the primary efficacy evaluation period for treatment j will be calculated as follows $\begin{aligned} \mu_j^{*evaluation} &= (\mu_j^{*Week\ 40} + \mu_j^{*Week\ 44} + \mu_j^{*Week\ 48} + \mu_j^{*Week\ 52})/4 \\ &= \beta_0 + \beta_{baseline} * \mu_{baseline} + \beta_j + (\beta_{Week\ 40} + \beta_{Week\ 44} + \beta_{Week\ 48} + \beta_{Week\ 52})/4 + (\beta_j^{*Week\ 40} + \beta_j^{*Week\ 44} + \beta_j^{*Week\ 48} + \beta_j^{*Week\ 52})/4 + (\beta_{baseline*Week\ 40} + \beta_{baseline*Week\ 44} + \beta_{baseline*Week\ 48} + \beta_{baseline*Week\ 52}) * \mu_{baseline}/4 \end{aligned}$ • The treatment difference for model based mean Hgb during the primary efficacy evaluation period will be calculated as follows $\begin{aligned} \mu_{daprodustat}^{*evaluation} - \mu_{epoetin}^{*evaluation} &= \beta_{daprodustat} - \beta_{epoetin} + (\beta_{daprodustat*Week\ 40} + \beta_{daprodustat*Week\ 44} + \beta_{daprodustat*Week\ 48} + \beta_{daprodustat*Week\ 52})/4 - (\beta_{epoetin*Week\ 40} + \beta_{epoetin*Week\ 44} + \beta_{epoetin*Week\ 48} + \beta_{epoetin*Week\ 52})/4 \end{aligned}$ • P-value for non-inferiority test will be based on the following t test statistic (Mascha 2011):

$$t = (\mu_{\text{daprodustat*evaluation}} - \mu_{\text{epoetin*evaluation}} - \delta) / s$$

δ : non-inferiority margin (= -1.0 g/dL)

s : standard error of treatment difference

The non-inferiority p-value is the probability of observing a larger value of t in a t distribution with degrees of freedom of the estimate of treatment difference based on the Kenward-Roger method.

Model Checking & Diagnostics

- In case there is a problem with convergence of the unstructured (type=UN) variance-covariance, the following strategy will be examined.
 1. Use Fisher's scoring algorithm for the estimation method.
 2. Set Heterogeneous Toeplitz (type=TOEPH) structure for variance-covariance structure.
- In the event of that this model still fails to converge, alternative correlation structures may be considered such as type=CSH or CS.

Model Results Presentation

- The point estimates of LS mean Hgb during the primary efficacy evaluation period for each treatment will be presented with the associated standard errors and 95% CIs. For non-inferiority assessment at a one-sided significance level of 2.5%, the estimate of the treatment difference, standard error, its 95% CI, and non-inferiority p-value will be provided.
- Non-inferiority will be established if the lower limit of the 95% CI for the treatment difference (daprodustat - epoetin beta pegol) of the mean Hgb during the primary efficacy evaluation period is greater than -1.0 g/dL (i.e., a p-value is smaller than 0.025).
- Model based Hgb curve over time with 95% confidence band will be displayed graphically for each treatment.

Subgroup Analyses

- Treatment differences (daprodustat - epoetin beta pegol) of the mean Hgb during the primary efficacy evaluation period, standard error, and the associated 95% CIs will be provided by each subgroup (See Section 5.4.2).
- The subgroup analyses will be based on the ITT population.
- The same statistical analysis method (using MMRM described as above) will be applied to estimate the mean Hgb during the primary efficacy evaluation period for each subgroup. If there is a problem with convergence for a certain subgroup, the result of the subgroup will not be displayed.
- Graphical summaries for the treatment differences of the mean Hgb during the primary efficacy evaluation period and the associated 95% CIs will be produced using a forest plot.
- For prior ESA use, model based Hgb curve over time with 95% confidence band will be displayed graphically for each treatment.

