- Note that log-transformed values will be used for TSAT and hepcidin in the MMRM analysis. The LS means for treatment j at visit k and the adjusted treatment difference at visit k will be exponentially back-transformed to the original scale and provided as follows:

Adjusted geometric mean percent change from baseline = $100 * (\exp(\mu_{jk}) - 1)$
 Adjusted ratio for percent change from baseline = $\exp(\mu_{\text{daprodustat}*k} - \mu_{\text{epoetin beta pegol}*k})$

Model Checking & Diagnostics

- In case there is a problem with convergence of the unstructured (type=UN) variance-covariance, the following strategy will be examined.
 1. Use Fisher's scoring algorithm for the estimation method.
 2. Set Heterogeneous Toeplitz (type=TOEPH) structure for variance-covariance structure.
 3. In the event of that this model still fails to converge, alternative correlation structures may be considered such as type=CSH or CS.

Model Results Presentation

- For ferritin, serum iron, and TIBC, the adjusted mean change from baseline will be presented with the associated 95% CIs by treatment at each assessment visit. The adjusted treatment

difference (daprodustat – epoetin beta pegol) for change from baseline will also be presented with the associated 95% CI at each assessment visit.

- For TSAT and hepcidin, the adjusted geometric mean percent change from baseline will be presented with the associated 95% CIs by treatment at each assessment visit. The adjusted ratio (daprodustat / epoetin beta pegol) for percent change from baseline will also be presented with the associated 95% CI at each assessment visit.

Subgroup Analyses

- For all of the respective iron parameter, the above analysis will be repeated by baseline iron use and prior ESA use subgroup (See Section 5.4.2) in the same manner.
- The subgroup analyses will be based on the ITT and Efficacy PD population.
- If there is a problem with convergence for a subgroup, the result of the subgroup will not be displayed.

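### If the primary MMRM ends at the CSH or CS fallback, its model-based standard error can make the Weeks 40–52 interval too narrow; an empirical standard error and a fixed order of structures should be specified for that step (minor)

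*SAP*

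**What the plan says.** SAP section 7.1.5.1 models Hgb at every 4-week visit from Week 4 to Week 52, which is 13 visits, with an unstructured covariance. The treatment contrast is the equally weighted mean of the Week 40, 44, 48 and 52 differences. On inference it says: "The Kenward-Roger method for calculating the denominator degree of freedom will be used". The test statistic divides the distance from the -1.0 g/dL margin by the standard error of the contrast. The decision rule is "Non-inferiority will be established if the lower limit of the 95% CI for the treatment difference" lies above -1.0 g/dL, equivalent to a one-sided p-value below 0.025.

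If the unstructured fit does not converge, the section tries Fisher scoring, then heterogeneous Toeplitz (TOEPH). After that: "In the event of that this model still fails to converge, alternative correlation structures may be considered such as type=CSH or CS". It names no change of standard error, degrees of freedom or decision rule for this step, and no order between the two structures. Section 5.5 claims overall one-sided control at 2.5% and makes this test the gate to the superiority test.

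**The concern.** CS and CSH both give every pair of visits the same correlation, whether 4 or 48 weeks apart. If Hgb is more alike at neighbouring visits than at distant ones, the fitted correlation is an average over all lags. It is then lower than the true correlation among the four endpoint visits, which are only 4 to 12 weeks apart. The variance of a mean of four positively correlated values rises with their correlation, so the fitted standard error of the contrast is too small. Kenward-Roger is a model-based small-sample adjustment and does not protect against a wrong structure.

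The error favours declaring non-inferiority. In this branch the interval compared with -1.0 g/dL would be too narrow, and the gate would operate above its stated level.

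**Working it through.** **Inputs from SAP 7.1.5.1:** one-sided level 2.5%; 13 visits; contrast weights of 1/4 on the last four visits; CSH or CS as the last step. From section 2.3: about 286 ND subjects, randomized 1:1. **Assumed:** the true within-subject correlation, the variance over visits and the dropout rate, none of which the SAP gives.

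**Stated figure.** With a correct standard error, 1 − Φ(1.960) = 0.0250, which reproduces the 2.5%.

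**Formula.** With complete data the point estimate is the same under any structure, because every term has its own visit-level coefficient. Only the standard error changes. With constant variance,

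ratio = fitted variance / true variance = (1 + 3·r₁₃) / (1 + 3·r₄),

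where r₁₃ is the mean correlation over all pairs of the 13 visits and r₄ the mean over pairs of the last four. The large-sample one-sided error is Φ(−1.960·√ratio).

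**Worked case, AR(1) with correlation 0.7 per visit.** r₄ = (3×0.7 + 2×0.49 + 0.343)/6 = 0.5705 and r₁₃ = 0.2901. Ratio = 1.8704/2.7115 = 0.690 and √ratio = 0.8305. Error = Φ(−1.628) = 5.2%.

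**Other correlation patterns, constant variance:**

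| True correlation | One-sided error |
|---|---|
| AR(1) 0.5 / 0.6 / 0.7 / 0.8 / 0.9 | 5.2 / 5.3 / 5.2 / 4.7 / 3.7% |
| Constant component 0.2–0.3 plus AR(1) 0.5–0.9 | 3.3–4.2% |
| Linear decline from 0.7 at 4 weeks to 0.4–0 at 48 weeks | 3.0–3.9% |
| Equal at all lags (CS true) | 2.5% |

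**Variance changing over visits.** The fitted variance under CS is then the average variance over the 13 visits; CSH keeps a variance for each visit.

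| True correlation | SD change, first to last visit | CS | CSH (approx.) |
|---|---|---|---|
| AR(1) 0.7 | +20% | 6.4% | 5.2% |
| AR(1) 0.7 | +40% | 7.3% | 5.2% |
| AR(1) 0.7 | −20% | 3.8% | 5.2% |
| AR(1) 0.9 | −20% / −30% | 2.6% / 2.0% | 3.7% |
| 0.2 constant plus AR(1) 0.8 | −20% / −30% | 2.8% / 2.1% | 4.0% |

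**Simulation check.** REML fit with CS, model-based standard error, 130 per arm, true difference exactly −1.0, 3,000 trials per scenario (Monte Carlo error about 0.4 percentage points). AR(1) 0.7 gave 5.4% without dropout and 6.2% with 20% random dropout. AR(1) 0.8 gave 4.9% in both. AR(1) 0.9 without dropout gave 3.5%. In the first case the true SD of the estimate was 0.1037 and the mean reported standard error 0.0848, a ratio of 0.82, in line with the formula. With a sandwich standard error on the CS fit, the error was 2.3–3.0%.

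**The case against.** **The branch is remote.** The unstructured fit, Fisher scoring and TOEPH must all fail first, with about 286 subjects planned. The SAP only says CSH or CS may be considered. This stands, and it is the main reason the point is minor. The route is nevertheless written into the confirmatory analysis, and following it can give a wrong interval.

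**The size rests on assumption.** A reader might infer that the error simply doubles. The documents do not support that: about 5% is near the upper end for constant variance, several plausible patterns give 3–4%, and true CS gives 2.5%. Since subjects are titrated toward a target range, a narrowing spread is plausible, and under CS the inflation can then disappear or reverse. CSH does not benefit from that.

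**The decision would rarely change.** Assume an SD of 1.0–1.5 g/dL for the subject mean and 130 per arm. The standard error of the difference is SD × √(2/130), or 0.124–0.186. An 18% shortfall moves the lower limit by 1.96 × 0.18 × that, or 0.04–0.07 g/dL, against a margin of 1.0. Power at a true difference of zero exceeds 99%. This stands, although type I error is defined at the margin.

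**The ANCOVA offers a check.** It uses one mean per subject and needs no within-subject covariance. It is supplementary and run in the mITT and PP populations, so it would expose a discrepancy but cannot replace the primary test.

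**The iron-parameter model.** Section 7.3.5.1 carries the same wording, "alternative correlation structures may be considered such as type=CSH or CS", so a reader might extend the point there. It does not carry over: those contrasts are at single visits, so averaging adjacent visits plays no part, and the analyses are not confirmatory.

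**Conclusion.** The point holds as a minor one, confined to the CSH/CS step of section 7.1.5.1. If that step is reached and the true correlation falls with lag, the model-based standard error of the Weeks 40–52 difference is usually too small. One-sided error is then roughly 3–5% with constant variance, and about 6% with 20% dropout or an SD rising by 20% under CS (more with a steeper rise), in place of 2.5%. Under CS, but not CSH, falling variance can cancel or reverse this. All these figures rest on assumed correlations and variances.

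The documents do not support reading this as a failure of error control in the planned analysis. The unstructured model is unaffected, and TOEPH gives 2.5% in large samples when correlation depends only on lag.

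**What to change.** Add to section 7.1.5.1: if CSH or CS is used, the confidence interval and non-inferiority p-value are based on the empirical (sandwich) standard error with between-within degrees of freedom in place of Kenward-Roger. Replace the open-ended list with a fixed order, CSH before CS. TOEPH and section 7.3.5.1 can stay as they are.

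The cost is a short addition to the text and one SAS option. The Kenward-Roger correction is lost in that branch, which is negligible with about 280 subjects. The sandwich estimator repairs the standard error only. It does not remove bias in the point estimate that a wrong covariance can cause when dropout is missing at random.
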